3.1 Background

In 2020, an estimated 8.4% of the world's 10 million TB cases occurred in Indonesia, making it the country with the third highest number of cases globally. (World Health Organization, 2021)

The country is a WHO high-burden country for TB, multidrug-resistant TB and TB/HIV. (World Health Organization, 2021) Yogyakarta province, located in central Java, Indonesia's most populated island, notified 3 802 cases in 2018 for an estimated case detection rate of 34.2%. Against the background of COVID-19 disruption in 2021 this fell to 2 963 notified cases and an estimated case detection rate of 32%. There are multiple challenges to improving case detection in Yogyakarta including limited active case finding (ACF) among high-risk populations for TB, high proportion of people with symptoms suggestive of TB do not seek care or do not get tested, and a low coverage of GeneXpert testing for TB.

The Zero TB Yogyakarta Initiative commenced community active TB case finding in 2020 with a pilot in 2 sub-districts in the province. The Zero TB Initiative Yogyakarta is a collaboration between the Universitas Gadjah Mada, the Burnet Institute (Melbourne), the Yogyakarta TB program and local partners and stakeholders. In 2021, Zero TB Initiative Yogyakarta commenced scaling up active case finding to 2 regencies (Kulon Progo and Yogyakarta City) funded by the PRIME-TB project (Papua New Guinea and Republic of Indonesia for Microelimination of TB, an Australian department of foreign affairs and trade (DFAT) Centre for Health Security funded project). Kulon Progo is predominantly a rural context with a population of 442 382. From August 2022, case finding in Sleman District will be commenced and active case finding in Kulon Progo will be scaled down.

3.2 Current Active Case Finding (Standard of Care)

Active TB case finding is community-based and utilises mobile chest X-ray units deployed in vans. Screening sites are chosen based on identification of potential 'hotspots' through mapping of reported cases over the past 3 years. Prior to a mobile screening event, the local health authorities and community leaders are consulted and information is disseminated to the community to invite those living close in potential 'hotspots' to attend a free TB screening, with information given of what is provided and where to attend. The mobile van teams conduct screening with COVID-19 safe precautions and can screen 80-120 people per day. Each person attending is screened using a symptom checklist to check for: cough for more than 2 weeks; fever; night sweats; weight loss/failure to thrive; and haemoptysis. In addition, all persons over the age of 5 receive a chest Xray (CXR) on the van. The CXR is read by qXR, a computer aided detection software. Persons may screen positive based on either their reported symptoms or their CXR, which are suggestive of TB. Spot sputum sample collection is attempted from all individuals who screen positive. Samples are then transported as a batch to a central laboratory for GeneXpert testing.

LOCATE TB Research Protocol v1.1 (2022-08-25)

Additionally, active case finding services include screening of household contacts. Newly registered TB cases are visited, and household members are screened for symptoms; for latent TB infection with a tuberculin skin test if eligible; and referred for a CXR at the mobile van services or nearest CXR facility.

Referral of sputum specimens centrally leads to delays in diagnosis and required extra visits from healthcare workers to follow up and contact patients with TB. Provision of TB molecular testing capacity within the mobile screening service could reduce diagnostic delays, reduce diagnostic loss to follow up and increase community acceptability.

3.3 Molbio Truenat Mtb Plus and MTB-RIF Dx

Molbio Truenat MTB Plus and MTB-RIF Dx (Truenat) are chip-based point-of-care rapid molecular assays for the detection of tuberculosis. The Truenat MTB Plus assay uses two devices — the first to extract and purify DNA (Trueprep Auto v2 Universal Cartridge-based Sample Prep Device) and the second (Truelab Real Time micro PCR Analyzer) to conduct PCR analysis to report a semi-quantitative result for MTBC. A positive sample can be loaded onto an additional chip (MTB-RIF Dx) for detection of rifampicin resistance. The Truelab Micro PCR Analyzer is portable, battery-powered and can provide a result in an hour. FIND's "real-world" multicentre diagnostic accuracy study has reported that "Truenat MTB, MTB Plus and MTB-RIF Dx assays have similar accuracy to Xpert MTB/RIF and can be performed at the primary healthcare centre level". (Penn-Nicholson, et al., 2021)

The Truenat MTB Plus and MTB-RIF Dx assays are WHO-endorsed with recommendations for use in adults and children with signs and symptoms of pulmonary TB. In the real-world multicentre study Truenat was reported as having a pooled sensitivity of 80% (75–84) and 96% (95–97) specificity when performed at primary health centres. (Penn-Nicholson, et al., 2021) In a comparison from sites where Truenat assays were conducted in parallel with GeneXpert MTB/RIF on the same specimens the authors reported no significant difference irrespective of smear status. (Penn-Nicholson, et al., 2021)

Devices	Throughput per 8-hour shift with optimized work flow ³	Estimated throughput with "real-world" conditions
1 Trueprep Device + 1 Truelab Analyzer Uno	10-12 specimens	7-9 specimens
1 Trueprep Device + 1 Truelab Analyzer Duo	20-24 specimens	15-18 specimens
2 Trueprep Devices + 1 Truelab Analyzer Quattro	40-48 specimens	30-36 specimens

TRUENAT DEVICE COMBINATIONS AND SAMPLE THROUGHPUT

The Truenat PCR Analyzer is able to transfer data wirelessly in real time using a SIM card, WIFI or Bluetooth. Results can be sent by SMS or email to clinicians as well as to electronic patient and lab information systems (via a customised API), or through extraction of the data in text delimited format. The analyser can store up to 20 000 results in internal memory

Chips (at temperatures between 2°C and 30°C) and the sample preparation reagents (at temperatures between 2°C and 40°C) have a shelf-life of 2 years. The chips can be stored for up to 6 months at temperatures between 30°C and 40°C.

No air intake is required for the devices and they are therefore dust-resistant, although a dustfree operating environment is still recommended and the devices should be situated away from sources of electromagnetic interference and vibrations. They are quoted as being able to operate in relative humidity ranging between 10% and 80%.¹

The in-built battery is cited as allowing for testing without power for up to 8 hours with batterylife specified as 5 years. Time to charge the analyser is quoted as 4 hours and 9 to 10 hours for the Trueprep device.

The portability and characteristics of Truenat MTB Plus and MTB-RIF Dx have the potential to enable point of care testing for TB, which could support TB diagnosis within primary health care services and within active case finding. This has the potential to reduce diagnostic delays and pre-treatment loss to follow up. However, the process for running the assay does rely on having trained, dedicated and skilled technicians.

4 Research Objectives

4.1 Primary objective(s)

 Assess the operational feasibility and acceptability of use of Truenat MTB Plus and MTB-RIF Dx (Truenat) within community TB case finding service in rural Yogyakarta, Indonesia

¹ https://stoptb.org/assets/documents/resources/publications/sd/Truenat_Implementation_Guide.pdf LOCATE TB Research Protocol v1.1 (2022-08-25)

4.2 Secondary objectives

- 2. Comparison of decentralised Truenat to centralised Xpert testing within community mobile TB case finding service for median time to result for those tested
- 3. Comparison of decentralised Truenat versus centralised Xpert testing for median time to commence treatment for bacteriologically confirmed TB cases

5 Methodology

5.1 Study Design

This is a prospective mixed-methods implementation science study to evaluate the use of Truenat MTB Plus and MTB-RIF Dx (Truenat) within a mobile active case finding service. Specific methods will be used for each of the endpoints under the primary objective.

For the **primary objective**, operational performance will be assessed through laboratory staff and health care worker Truenat proficiency assessments after initial training (1a), and measurement of platform error rates during the study (1b). Views on the acceptability and operational challenges of Truenat will be assessed by a survey of laboratory staff and health care workers (HCW) within the program (1c). Individual in-depth qualitative interviews will be conducted with a purposive sample of screening participants to obtain their views on the acceptability and suitability of decentralised testing using Truenat (1d). The purposive sampling of screening participants will deliberately target the inclusion of participants representing a diversity of sex, age, microbiological positivity, and risk populations.

For the **secondary objectives**, a randomised comparison of decentralised microbiological testing using Truenat Mtb Plus and MTB-RIF Dx compared with standard of care centralised GeneXpert testing will be conducted. Screening days will be randomised 1:1 to the Truenat or standard of care, and the participants screened on those days then being assigned to corresponding study arm (Truenat arm or standard of care arm). Randomisation will be done across screening days within 2-week blocks for case finding activities. Only management staff will be informed in advance of the assignment for screening days to organise staff schedules. Community mobilisation will be done by the community cadre who will not know which screening type is being performed on any specific day, to reduce the potential for people in the community preferentially choosing a screening day based on which test will be available.

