'hotspot' sites for screening are identified based on TB program records of previously reported TB cases within the preceding 3 years. Designated sites for screening are identified more than 2 weeks in advance to allow time to notify relevant authorities and the community near the intended screening site of the service and the free access to screening for TB, with community mobilisation by trained community cadres in consultation with the Dinas Kesehatan. Screening consists of symptom screening and CXR with computer aided diagnosis (CAD) software reading of CXR using qXR software. Those who screen positive based on symptoms or abnormal CXR (qXR interpretation) during screening have a spot sputum collected for molecular testing.

Household contacts of microbiologically confirmed cases are screened for symptoms and with tuberculin skin testing and also referred for CXR by mobile screening or at the nearest CXR facility. Household contacts who screen positive based on symptoms or CXR will have a spot sputum sample collected for molecular testing.

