The mobile service screens 1000 people per month with 12.1% of participants in rural areas screening positive and requiring microbiological examination of sputum samples. We will enrol participants for a minimum of 6 months and a maximum of 9. Which would result in between 3000–4500 persons screened in each arm. Consequently, per the calculations below, the sample will be sufficiently powered to detect a difference in median time to result of one or more days with an alpha of 0.05 and power of 0.8. This would require a minimum of 211 microbiological examinations in each arm. Throughput in of 3000–4500 persons would be expected to result in 363–544 microbiological examinations in each arm.

Median time to result standard of care	Median time to result Truenat	Alpha	Power	Sample size per arm
3 (sd = 14)	1 (sd = 14)	0.05	0.8	29
3 (sd = 21)	1 (sd = 21)	0.05	0.8	34
3 (sd = 14)	2 (sd = 14)	0.05	0.8	175
3 (sd = 21)	2 (sd = 21)	0.05	0.8	211

These assumptions are based on the current active case finding TB diagnostic cascade from the PRIME-TB/TB REACH project in Yogyakarta in 2020 and 2021, which includes the impact of COVID-19 on activities.

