For study participants who are tested using a TB molecular diagnostic test, the median time from sample collection to result will be calculated and a test of significance will be performed on the medians from the standard of care group and the Truenat group. The expected number of patients diagnosed with bacteriologically confirmed TB is expected to be too small to give sufficient power to detect a difference in median time to treatment start in these patients. Nonetheless, the median time from sample collection to treatment initiation will be calculated for the two groups. Time to event analyses will be described by Kaplan-Meier-curves by diagnostic arm. Details will be presented in the Statistical Analysis Plan.

Interquartile ranges (IQRs) and box and whisker plots will be generated for all medians, with differences in medians compared using the Wilcoxon signed rank test (Mann-Whitney *U*). Interim data analysis will occur at the study mid-point, with results reviewed by the study team.

Endpoint	Numerator	Denominator	Data source
Objective 1	 		 
Proportion of	Staff trained	All staff trained	Post training assessment
staff trained who	achieving		
were deemed	proficiency in post		
proficient	training assessment		
Proportion of	Number of Truenat	Number of	Mobile ACF service error
tests performed	tests with error or	Truenat tests	form
with an error	invalid result	performed	
Proportion of	Time (hours and	Time (hours and	Mobile ACF service
time of device	minutes) of device	minutes) during	laboratory availability
unavailability for	unavailability during	screening days	records
use during	Truenat screening	when Truenat	

TABLE 1: ENDPOINTS AND DATA SOURCES

working day	days for any reason	randomized to be	
		available	
Objectives 2 and 3			
Madian tinga ta		Γ	Activo caso finding
Median time to			Active case midning
diagnostic test result			database (Redcap)
for participants			Laboratory database
tested with a TB			
molecular diagnostic			
test			
Median time to			Active case finding
treatment			database
initiation for			Deeleenee Deteleen
participants with			Pusksemas Database
an initial positive			Week-1 telephone call
result on a TB			
molecular			
diagnostic test			

Mixed-Methods Analysis and Outputs

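### Two-week blocks of about 4-6 screening days in an open trial make some late-block days predictable to field staff, and the named test uses neither the day nor the block

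*Protocol*

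**What the plan says.** **Allocation.** Section 5.1: "Screening days will be randomised 1:1 to the Truenat or standard of care", and "Randomisation will be done across screening days within 2-week blocks for case finding activities". It does not give the number of screening days in a block, whether each block must split equally, what happens when a block has an odd number of days, or whether block length varies.

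**Concealment.** Section 5.1: "Only management staff will be informed in advance of the assignment for screening days to organise staff schedules". It adds: "Community mobilisation will be done by the community cadre who will not know which screening type is being performed on any specific day". The stated aim is to keep people from picking a day by the test on offer.

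**Visibility of the arm.** Under section 5.4.2, Truenat participants give two sputum samples, are tested on site and may wait for the result. Standard-of-care samples go to a central laboratory. Consent is sought on site that day from people who screen positive.

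**Throughput.** Section 5.9.2: "The mobile service screens 1000 people per month". Section 3.2 says the van teams "can screen 80-120 people per day".

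**Lead time.** Section 5.3: "Designated sites for screening are identified more than 2 weeks in advance to allow time to notify relevant authorities and the community".

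**Analysis.** Section 5.10.2 compares the arms "with differences in medians compared using the Wilcoxon signed rank test". The parenthesis that follows names the Mann-Whitney U, so I read it as the unpaired rank test on individuals. No day or block term is given, and further detail is left to a SAP that is not at hand.

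**The concern.** With short balanced blocks and a visible arm, the last assignments of a block follow from the earlier ones by counting, with no access to the list. Section 5.1 protects against advance knowledge only by restricting who is told, and counting gets round that.

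The people best placed to count are field staff. Household contacts belong to the trial population, and section 3.2 has them referred for chest X-ray at the van or the nearest facility. No section fixes the day on which they come. A staff member who expects a Truenat day could direct a contact, or someone who will return, to that day. This would change who enters each arm, which is separate from selection at consent.

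The second issue is that the day is what is randomised, while the named test treats each participant as independently allocated. People screened on one day share a sample batch, transport, laboratory queue and staff. The comparison is the study's only between-arm evidence, and section 6.4 expects the study to inform government decisions on scale-up.

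**Working it through.** **1. The plan's own figures.** Expected examinations per arm: 3000 × 0.121 = 363 and 4500 × 0.121 = 544.5, matching the stated 363-544. The minimum of 211 per arm also reproduces, with a log-normal formula for individually randomised participants:

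- σ² = ln[(1 + √(1 + 4(SD/median)²))/2]. For median 3, SD 21 this is 2.017; for median 2, SD 21 it is 2.399.
- n = (2.017 + 2.399) × (1.960 + 0.842)² / [ln(3/2)]² = 4.416 × 7.849 / 0.1644 = 210.8, so 211.

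The formula has no day or block term.

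**2. Days per block.** Days per fortnight = (1000 / people per day) × 14/30.44.

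| People per day | Days per month | Days per 2-week block | Days in 6 months |
|---|---|---|---|
| 120 | 8.3 | 3.8 | 50 |
| 100 | 10.0 | 4.6 | 60 |
| 80 | 12.5 | 5.7 | 75 |
| 60 (assumed) | 16.7 | 7.7 | 100 |
| 40 (assumed) | 25.0 | 11.5 | 150 |

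The first three rows use the stated range. The last two show attendance below capacity.

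**3. Predictability if each block is balanced n:n.** The observer has seen every earlier day of the block.

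- Share of days known with certainty = 1/(n+1).
- Share guessed correctly, always guessing the arm that is behind = [n + 2^(2n−1)/C(2n,n) − 0.5]/(2n).

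| Block | Certain | Guessed correctly (chance is 50%) |
|---|---|---|
| 2:2 | 1/3 = 33% | (2 + 8/6 − 0.5)/4 = 71% |
| 3:3 | 1/4 = 25% | (3 + 32/20 − 0.5)/6 = 68% |
| 4:4 | 1/5 = 20% | (4 + 128/70 − 0.5)/8 = 67% |
| 5:5 | 1/6 = 17% | (5 + 512/252 − 0.5)/10 = 65% |

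Listing all balanced sequences gives the same values.

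**4. Number of deducible days in 6 months,** pairing each block size with the throughput that produces it: 50 × 1/3 = 16.7 (120 a day, 2:2) and 75 × 1/4 = 18.8 (80 a day, 3:3), so about 17-19.

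**5. Type I error of the unstratified Mann-Whitney test at nominal 5%.** Simulated with 13 balanced blocks, 4 days of 15 screen-positives or 6 days of 10, and 1500 runs per setting. The intraclass correlations (ICC) are assumptions; the protocol gives none.

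| Source of correlation | 4-day blocks | 6-day blocks |
|---|---|---|
| None | 4.9% | 4.5% |
| Block only, ICC 0.05 / 0.10 / 0.20 | 4.3 / 4.0 / 2.7% | 3.4 / 3.8 / 2.9% |
| Day only, ICC 0.05 | 15% | 9% |
| Day only, ICC 0.20 | 30% | 22% |
| Block 0.10 and day 0.10 | 21% | 16% |

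**6. What varied lengths achieve.** Take lengths of 4, 6 or 8 days in random order and an observer who knows those three lengths and has seen every day. In 1500 simulated lists of 60 days, certain days fall to about 2%. Guessing the arm that is behind needs no knowledge of where blocks end, so its rate barely moves: (2.83 + 4.10 + 5.33)/18 = 68%. Longer blocks lower it only slowly; a known 16-day block gives 63%, with 11% of days certain.

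**The case against.** **The premises are partly inferred.** Equal splits are not stated, nothing says field staff are told the scheme, and 80-120 a day is a capacity. This stands, so the percentages are conditional. Balance is nevertheless the natural reading of 1:1 within blocks. If it is not intended, the text should say what the blocks do.

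**A reader might infer that the cadres' blinding is defeated.** The documents do not support that. Sites are set and communities notified more than two weeks ahead, which is longer than a block, so much mobilisation would come before the block's earlier days are seen. No section says cadres learn which arm ran at other sites. Several teams or vans may also mean that no one person sees every day.

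**Staff know the arm at consent anyway.** True at any block length, and the fix does not change it. That affects who consents among people already present; predictability affects who comes on which day.

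**The bias route is weak for the main comparison.** Time from sample to result depends mostly on test location and laboratory logistics, and steering patients would not obviously shift it much. Time to treatment is more exposed, but section 5.10.2 already calls it underpowered. This stands.

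**The analysis belongs to the SAP.** Details are deferred, but the protocol itself names the test. A reader might conclude that leaving out blocks makes the intervals too wide. That is only half the picture: block omission alone is conservative, while day-level clustering pushes the other way.

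**Conclusion.** The point holds as a weakness, not as a failure of concealment. If blocks are balanced and teams run at the stated capacity, 25-33% of days (about 17-19 in 6 months) are deducible by staff who saw the earlier days of the block, and 68-71% are guessable. With lower attendance the shares fall slowly, to about 17% and 65% at 5:5. The most plausible route is staff directing household contacts or returning attendees to a particular day. The documents do not show that this would materially bias time to result.

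On the analysis, the named test uses neither the randomised unit nor the blocks. Its direction of error depends on correlations the protocol does not give. Blocks alone take the size to 2.7-4.3%, whereas a day effect of 0.05-0.20 takes it to 9-30%. Of the two omissions, the screening day matters more.

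**What to change.** **Section 5.1.**

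- Use a computer-generated 1:1 list of screening days with randomly varied block lengths, for example 4, 6 or 8 screening days, not tied to the calendar fortnight.
- Do not disclose the lengths to field staff or cadres.
- Have the list held outside the field team, for instance by the data manager, and release each assignment only as early as rostering and device charging require. Section 3.3 quotes 9-10 hours to charge the Trueprep device.

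An 8-day block spans about 2.8-4.2 weeks (8/5.75 × 2 to 8/3.83 × 2), so calendar balance is largely kept. A 16-day block would span about 5.6-8.4 weeks and give up more of it.

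**Section 5.10.2.** Compare the arms with the screening day as the unit, for example by a re-randomisation test that permutes days within the blocks actually used. This accounts for both day and block.

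**Cost.** A short amendment and a new list from existing software, with no extra participants or staff. Balance within a single fortnight is slightly looser and rosters a little less even. Varied short blocks remove nearly all certainty but leave guessing at about two in three, and selection at consent remains.

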5.2 Participants

5.2.1 Primary objectives

The participants in the post-training proficiency assessments (objective 1a) will include laboratory staff and health care workers who have been trained to perform assays using the Truenat.

For the survey on acceptability and feasibility (objective 1c) all health workers and laboratory staff involved in screening and testing using Truenat will be invited to complete the survey.

For the qualitative interviews on Truenat acceptability for individuals being screened (objective 1d), participants will be individuals who have been screened using the Truenat strategy no more than 1 week prior to the interview. Individuals will be purposively sampled to capture perspectives of people residing in different areas; with different characteristics (age, gender); and with different results (positive and negative test results). To include perspectives relevant to the use of the Truenat strategy for children we will interview the parents or guardians of children.

